5.3 Enrollment and Baseline Assessment

Screening

The investigator or designated research staff will perform an evaluation of the study candidate for study eligibility, which may include a history and physical examination of the nasal area, review of overall medical history, understanding of general health and discussion of any conservative measures used chronic rhinitis. In addition, patients will complete standard questionnaires to document current symptoms associated with chronic rhinitis (rTNSS, MiniRQLQ).

Patients must be diagnosed with chronic rhinitis prior to entry into the study. The use of diagnostic procedures and screening tests to determine a diagnosis and assess whether patients are appropriate candidates for inclusion in the study is an appropriate pre-entry activity. While the availability of the study may be discussed with a prospective participant without first obtaining consent, informed consent must be obtained prior to initiation of any clinical procedures dictated by the protocol that are performed solely for the purpose of determining eligibility to participate in the study. Once the pretreatment assessments are completed the study procedure should be scheduled within 30 days.

Informed consent

Informed consent must be obtained in accordance with FDA regulation 21 CFR Part 50 and ISO 14155. The clinical investigator or designated staff member is responsible for ensuring that IRB/EC approved informed consent is obtained for each participant prior to participation in the study or before undergoing any procedure specific to the clinical investigation. The patient must be fully counseled with an explanation of the study background, study procedure, followup schedule, and informed of their options, risks and benefits, and have every opportunity to ask questions about participation in the study. Any new information obtained during the course of the study that may affect the health of the participant or their decision to continue in the study will be provided to the participant. This process includes a thorough explanation of the informed consent document that the patient will be asked to sign acknowledging that they understand and desire to participate in the study. The explanation and discussion should be conducted in such a way as to:

- answer the participant's questions,
- avoid coercion or influence of patient to participate in the study,
- ensure the patient understands that their legal rights are not waived at any time,
- use language at a level the patient can understand, and
- ensure the patient understands that after providing signature on the Informed Consent, the patient may still withdraw at any time before, during or after study treatment.

Evaluation of inclusion and exclusion criteria

The Screening Visit / Study Eligibility CRF will be used to document the participant's eligibility status.

Pretreatment (baseline) data and assessments

The following data will be obtained prior to treatment and recorded on the Baseline Visit Demographics and Treatment History CRF:

- Demographics
 - o Sex
 - Height (inches)
 - Weight (pounds)
 - Date of birth
 - Race / Ethnicity
- Nasal symptoms, history of treatments, nasal visual exam
 - History (duration) of rhinitis

- Rhinitis triggers (allergic or nonallergic)
- Medications used to treat rhinitis
- Previous ENT treatments
- Turbinate enlargement, nasal polyps, and other significant findings

The nasal assessment data (each nostril) including photos or video (physical and endoscopic) will be recorded and entered into the eCRF.

Current use of medication, devices, or other therapies for symptoms of chronic rhinitis, including medication name, frequency, and dose will be detailed on the Medication Log.

Rhinitis symptom severity, including the rTNSS, cough and postnasal drip, will be completed by the participant on the rTNSS CRF.

The MiniRQLQ will be completed by the participant on the MiniRQLQ CRF.

5.4 Treatment Visit and Procedure

If the participant meets eligibility criteria and signs the IRB/EC approved informed consent the participant is considered enrolled.

The treatment procedure is summarized below. Consult the RhinAer Stylus and Aerin Console Instructions for Use (IFUs) for full detail of the treatment procedure and step-by-step instructions for preparation and use of the RhinAer Stylus and Aerin Console.

Preparation

The procedure will be performed in the study clinic. The participant will be in a reclined or supine position on the procedure table. A visual physical and endoscopic nasal assessment will be conducted just prior to the procedure and documented on the appropriate CRF. The study physician will map out the treatment area by evaluating the middle meatus and surrounding structures of the nasal cavity to understand access of the study device to the mucosal area for treatment. Participants will have both PNN areas treated in a single study procedure session. Each nostril will be treated at up to 5 nonoverlapping positions within the posterior portion of the middle meatus and posterior portion of the inferior turbinate (Figure 4).

[figure not shown]

Figure 4. RhinAer Stylus in the nose.

The physician will anesthetize the treatment area by using a topical swab/gauze or spray of lidocaine to numb the mucosal tissue, wait a minimum of 20 minutes, and then inject anesthesia to the treatment area after initial numbness has occurred.

Treatment administration

An endoscope will be inserted into the nasal cavity so the physician can visualize the mucosal area of treatment. The RhinAer Stylus will then be inserted to access the treatment area. The Stylus will be connected to the Aerin Console generator and the RF energy level will be set on the generator.

The default settings for the RhinAer Stylus will be used for the study:

Temperature	60 °C
Power	4 Watts
Treatment Time	12 secs
Cooling Time	0 secs

The physician will apply the treatment tip of the RhinAer Stylus to the target tissue prior to energy delivery. The energy is turned on by maintaining downward pressure on the foot pedal. With the energy on, the physician continues to apply the Stylus tip to the mucosal surface consistent with the IFU. A tone will be heard when energy is being delivered until the treatment is complete. After the treatment time is reached, the Aerin Console will cease to delivery energy and reset for subsequent treatments.

No repeat ("touch-up") procedures will be permitted during the study follow-up period.

Procedure data collection

Data relating to the procedure and the products used will be recorded on the Procedure CRF. The following information will be recorded:

• Date of procedure

- Preprocedure nasal assessment (each nostril) including photos or video (physical and endoscopic)
- Preprocedure and procedure medications
- RhinAer Stylus and Aerin Console information
- Aerin Console settings
- Procedure start and end times
- Number of sites treated
- Occurrence of device malfunction, protocol deviation, or adverse events.

5.5 **Postprocedure Assessments and Care**

An endoscopic nasal assessment will be conducted prior to discharging the participant and reported on the Procedure CRF.

Participants will be asked to indicate the pain level experienced during the study procedure from anesthesia delivery to procedure completion using the VAS pain score instrument (vertical line marked on the 100 mm line) on the Pain VAS CRF.

At the discretion of the physician, the following care may be provided:

- Apply compression to the treatment area internally for 5 minutes.
- Apply petroleum jelly to the treatment area as needed.
- Use of nasal saline spray or ointment as needed.
- The participant should be instructed not to blow their nose for 24 hours.

Participants should have their 3-month follow-up visit (13 weeks) scheduled within the visit window prior to release.

Participants should not generally receive other concomitant nasal treatment therapies or interventions after the procedure or during the study follow-up period to avoid confounding the evaluation of the effect of the treatment, unless the additional care is in response to an adverse event or is considered in the best interest of the participant. Therapies, interventions, and pain medication will be monitored at follow-up evaluations.

5.6 Follow-up Evaluations

Follow-up visit dates will be calculated from the study procedure date. Follow-up visits should be scheduled within the specified visit windows described in Section 5.1 and Table 1 (Section 8.3.2). The office follow-up evaluation occurs at 13 weeks after the procedure. Evaluations at 6, 12, 24, and 36 months will be conducted remotely by telephone assessment by site personnel. The timing of all follow-up evaluations is based on the date of the procedure and should not be altered based on the actual time of preceding follow-up visits. Participants who make nonstudy visits should be evaluated for possible adverse events and an Adverse Event CRF should be submitted if appropriate.

RhinAer RELIEF single arm protocol Rev C Final 27JAN2021CONFIDENTIAL

All participants should be followed through the final evaluation visit at 3 years postprocedure regardless of their success/failure classification at previous evaluations. Every effort should be made to avoid having participants withdraw from the study (Section 9.5). If a participant does choose to withdraw from the study, it is very important to record information regarding the reason(s) and the last known status of the participant.

The following assessments will be conducted as indicated for each follow-up time point and recorded on the corresponding CRFs:

Office evaluation at 13-week (3-month) follow-up

- Nasal assessment (each nostril) including photos or video
- Current use of medication, devices or other therapies for symptoms of chronic rhinitis, including medication name, frequency, and dose
- Participant reported change in use of as needed medications and devices for chronic rhinitis symptoms (completed by participant)
- rTNSS (completed by participant)
- Cough and postnasal drip symptoms (completed by participant)
- MiniRQLQ (completed by participant)
- VAS pain score (completed by participant)
- Adverse events.

Remote (telephone) evaluations: 6-month (26-week), 12-month (52-week), 24-month (104-week), and 36-month (156-week) follow-up

- rTNSS (verbal administration by site personnel)
- Cough and postnasal drip symptoms (verbal administration by site personnel) (no 2-week)
- MiniRQLQ (verbal administration by site personnel)
- Participant reported change in use of as needed medications and devices for chronic rhinitis symptoms (verbal administration by site personnel)
- Patient satisfaction survey (verbal administration by site personnel)
- Current use of medication or other therapies for symptoms of chronic rhinitis, including medication name, frequency, and dose (study staff follow-up required if participant indicates changes)
- Adverse events (study staff follow-up required if participant indicates changes).

5.7 **Product Handling and Accountability**

A system that allows tracking of orders, shipping and returns will be used to control RhinAer Stylus and Aerin Console inventory. The devices will be packaged and

labeled to clearly indicate that they are for clinical study use only and must only be used for participants enrolled in this study. All devices not used must be returned to the sponsor or disposed of in accordance with the sponsor's instructions. The investigator is responsible for adequate record keeping regarding the receipt, use, and final disposition of study inventory.

6.0 Statistical Considerations

6.1 Study Design

This is a prospective, multicenter, open-label, single-arm study to assess the performance of the RhinAer procedure for treatment of chronic rhinitis. The study is designed to assess improvement in rTNSS and other measures from baseline condition to 3 months after the procedure, as well as for extended follow-up through 3 years.

6.2 Study Hypothesis

The primary endpoint of the study is change in mean rTNSS from baseline to the 13week evaluation. Improvement in the rTNSS is represented by a decrease from baseline in the 12-point score.

An MCID of 1 unit, or 2 to 4 times the more rigorously derived MCIDs, was set for this study. The hypothesis is that the improvement (decrease) in rTNSS mean score, measured as change from baseline at 13 weeks (13 weeks - baseline), exceeds the MCID (1 unit).

The null (H₀) and alternative (H_A) hypotheses are:

 $H_0: \mu_d \ge -1$

H_A: $\mu_d < -1$

where μ_d = the mean change of the paired differences of the 13-week scores minus the baseline scores.

Rejection of the null hypothesis in favor of the alternative (H_A) hypothesis means that there is evidence for a clinically significant improvement (decrease) in the rTNSS.

6.3 Sample Size Estimate

The study will enroll up to 140 participants. The power analysis was performed such that there is adequate power to reject the null hypothesis that the mean improvement from baseline in rTNSS is 1 point or less. Sample size estimation was based on a paired t-test for change from baseline at 13 weeks using the following assumptions:

- Significance level $\alpha = 0.025$ (one-sided)
- Power = 90%
- $\mu_d = 1$ -point decrease in mean change score = MCID
- SD = 3 = estimated standard deviation of the mean difference based on an observed SD of 2.6 in a prior study.

RhinAer RELIEF single arm protocol Rev C Final 27JAN2021CONFIDENTIAL

The minimum number of subjects to achieve 90% power is 97 (G-Power, paired ttest). Allowing for 15% loss (nonevaluable) and adjusting for a balanced distribution across 20 sites the sample size is 140 participants. It is anticipated that participants will be enrolled at sites on a competitive basis; however, a reasonable balance of participants among sites may be maintained by potentially capping enrollment at individual sites based on the final number of participating sites.

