6.10 Primary Endpoint Analysis

The mean change in the rTNSS from baseline to 13 weeks will be tested using a paired t-test for a significant decrease greater than the MCID under the one-sided null and alternative hypotheses.

A *P* value for the test statistic \leq .025 will indicate that the mean decrease is statistically significantly greater than 1 point. The upper limit of the one-sided 97.5% confidence interval on the mean decrease will also be calculated.

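### Section 6.3 sets the assumed effect equal to the null boundary, so the stated 90% power belongs to no effect that the plan names for its primary test

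*Combined protocol and SAP*

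**What the plan says.** Section 6.2 sets H₀: μ_d ≥ −1 against H_A: μ_d < −1. It defines μ_d as "the mean change of the paired differences of the 13-week scores minus the baseline scores", which is the change itself and not its excess over the MCID. Section 6.10 applies the same test: P ≤ .025 "will indicate that the mean decrease is statistically significantly greater than 1 point".

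Section 6.3 describes the aim of the power analysis consistently with this, saying that "there is adequate power to reject the null hypothesis that the mean improvement from baseline in rTNSS is 1 point or less". Its list of assumptions is one-sided α 0.025, power 90%, SD 3 ("estimated standard deviation of the mean difference based on an observed SD of 2.6 in a prior study"), and μ_d equal to a 1-"point decrease in mean change score = MCID". From these it concludes: "The minimum number of subjects to achieve 90% power is 97". The last step reads: "Allowing for 15% loss (nonevaluable) and adjusting for a balanced distribution across 20 sites the sample size is 140 participants".

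Two other sections bear on the 15%. Section 6.5 defines the Evaluable Population as those enrolled and treated. Section 6.6 imputes a missing primary outcome as no change from baseline.

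**The concern.** The same symbol, μ_d, takes the value −1 both as the edge of the null hypothesis and as the effect at which power is claimed. Power at the edge of the null is the type I error rate. A reader who takes section 6.3 at its word would believe that the trial has a 90% chance of success if the true mean fall is 1 point, when the chance is 2.5%. No section states a larger assumed mean change, so nobody can tell which effect the 90% refers to.

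A linked ambiguity concerns the 15% loss. If these are untreated participants left out of the analysis, inflating enrolment is the right allowance. If some are treated participants with no 3-month score, section 6.6 keeps them in the test with a change of zero, which pulls the mean towards the null. Inflating enrolment does not undo that.

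**Working it through.** **Inputs.** One-sided α 0.025, power 90%, SD 3 (2.6 observed), listed change −1, minimum 97, loss 15% and total 140 come from section 6.3. The null value −1 comes from section 6.2. The 5.1-point fall in the earlier 50-participant study comes from section 1.0. SD 3 is read as the SD of individual changes; the reproduction of 97 supports that reading.

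**Formula.** For a paired t-test with n participants and a distance δ between the true mean and the null value, power = P(T > t₀.₉₇₅,ₙ₋₁), where T is noncentral t with n − 1 degrees of freedom and noncentrality λ = δ√n / SD.

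**Step 1: reproduce 97.** With δ = 1 and SD = 3:
- The normal approximation gives (3 × (1.960 + 1.282) / 1)² = 94.6, so 95.
- Noncentral t gives power 0.8985 at n = 96 and 0.9015 at n = 97 (λ = √97 / 3 = 3.28). The minimum is 97, as stated.
- Alternative inputs do not give 97: one-sided α 0.05 gives 79, two-sided 0.025 gives 115, and SD 2.6 gives 73.

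So 97 is right for a distance of 1 point from the null.

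**Step 2: use the listed μ_d with the planned null.** δ = |−1 − (−1)| = 0, so λ = 0. T is then central t, and power is α = 2.5% for every n.

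**Step 3: find what 97 can mean.** δ = 1 fits a true change of −1 tested against 0, or a true change of −2 tested against −1. Only the second is the planned test.

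**Step 4: power of the planned test (null −1).** 119 is 140 × 0.85.

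| Analysed n | True fall for 90% power, SD 3 | Same, SD 2.6 | Power at a 1.5-point fall, SD 3 | Power at a 2.0-point fall, SD 3 |
|---|---|---|---|---|
| 97 | 2.00 | 1.86 | 37% | 90% |
| 119 | 1.90 | 1.78 | 44% | 95% |
| 140 | 1.83 | 1.72 | 50% | 97% |

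At a 5.1-point fall power is about 100% in every row.

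**Step 5: the 15%.** The documents give no expected rate of missing 3-month scores, so this is an illustration at a true fall of 2.0 points.
- If all 15% are untreated and excluded, 119 are analysed with none imputed, and power is 95% (SD 3).
- If instead 7, 14 or 21 of 140 (5%, 10%, 15%) are set to zero change, simulation with 200,000 runs gives 95%, 91% and 83% at SD 3, and 99%, 97% and 92% at SD 2.6.
- Rough check of the 15% case at SD 3: mean fall 0.85 × 2 = 1.7; variance 0.85 × (9 + 4) − 1.7² = 8.16, so SD 2.86; with n = 140 and δ = 0.7, power is 82%.
- At a true fall of 5.1 points all cases remain about 100%.

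**Step 6: from 97 to 140.** 97 / 0.85 = 114.1, so 115. An equal number at 20 sites gives 6 × 20 = 120. The total of 140 equals 7 × 20.

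**The case against.** The strongest reply is that nothing was miscalculated: 97 is correct for a 1-point distance, and the author may have meant an excess of 1 point over the MCID. That may well be the intention, but section 6.3 equates the value with the MCID itself, and section 6.2 defines μ_d as change from baseline. The reading has to be supplied by the reader.

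A second reply is that the sponsor plainly expects more than a 1-point fall. Section 6.11 expects at least 60% responders at 30% improvement, and entry requires rTNSS ≥ 6, so a responder falls by at least 1.8 points. As an illustration, with normal changes, SD 3 and everyone at baseline 6, 60% responders implies a mean fall of about 1.8 + 0.253 × 3 = 2.6 and power of 99.9% at n = 97. This makes the 1.5-point scenario look remote. It does not supply the missing assumption, because it is inferred from a secondary endpoint and states no mean change.

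Third, the imputation figures rest on a chosen effect and chosen missing rates. The 119-analysed case also assumes that the primary test uses the Evaluable Population, which section 6.10 does not say. If all enrolled participants were analysed, untreated ones could be imputed too. These limits stand, and the figures are conditional. The no-change rule is prespecified and works against the device.

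Finally, the plan already calls 140 an upper limit and attributes the increase to site balance. Only the intermediate step is unshown, and the surplus does not reduce power.

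**Conclusion.** The point holds. At the effect listed in section 6.3, the planned test has 2.5% power, not 90%. The figure of 97 corresponds to a true fall of about 2.00 points tested against −1 at SD 3 (1.90 with 119 analysed, 1.83 with 140), and the documents state no such effect. These results assume roughly normal changes, the section 6.3 SD and no imputed values.

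The fault is in the stated assumption and hence in the stated power, not in the design. Type I error is unaffected. If the true fall is near the earlier study's 5.1 points, power is about 100%, even with 15% imputed as no change. It is worth correcting because it is the only power statement in the plan. The meaning of nonevaluable is a lesser, conditional matter: at a true fall of 2.0 points and SD 3 it separates 95% from 83% power.

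**What to change.** In section 6.3, list the null value and the assumed true effect on separate lines, and restate the power for the latter. For example: *Null value: mean change −1 (the MCID). Assumed true mean change: [sponsor's value and its source]. With SD 3 and one-sided α 0.025, [n] evaluable participants give 90% power.* The sponsor should choose and justify the value; the table above shows what 97, 119 and 140 can detect.

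In the same section, say whether the 15% nonevaluable are untreated participants or participants without a 3-month score. If any are the latter, give the power under the section 6.6 imputation. A short clause showing how 140 is reached (7 at each of 20 sites) would complete the derivation.

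The cost is a few sentences in section 6.3. No extra participants are needed, and the sample size, test and alpha stay as they are.

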6.4 Timing of Analysis

The primary evaluation phase of the study lasts until all participants have reached the primary endpoint at 13 weeks (3 months) postprocedure. The primary and secondary endpoints will be analyzed using the data from the primary evaluation phase for an interim study report when these data become available. Informational outcomes will be analyzed and included in interim reports after all participants have reached each of the successive follow-up time points. A final study report will be provided after all participants have reached the final follow-up evaluation of the extended follow-up phase of the study.

6.5 Analysis Populations

Enrolled Population – all subjects enrolled in the study.

Evaluable Population – all subjects that are enrolled in the study and have received the study procedure.

Safety Population – all subjects enrolled in the study.

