6.8 Participant Disposition

A detailed description of participant disposition will be provided using a CONSORT diagram and summaries of participants falling in various subgroups of interest, such as, enrolled but not treated, discontinued, protocol deviations, deaths, and withdrawals. All study population exclusions and reasons will be summarized. Follow-up by visit will be presented, showing theoretical, expected, and actual follow-up visits.

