6.13 Safety Analysis

All adverse events will be analyzed for all participants. Adverse events will be coded using a custom Aerin Medical dictionary so that adverse events may be categorized for analysis at an appropriate level of detail. Listings will be provided to detail individual events. The number of participants, number of AEs, and the proportion of participants reporting each AE will be summarized. Seriousness and severity of AEs and their relationship to the device and procedure will be summarized. A time course of adverse events will be presented. Any unexpected adverse device experiences or adverse events that occur at an unexpectedly high incidence rate will receive detailed analyses. Narratives will be presented for all deaths, serious adverse events, unexpected adverse device experiences, and participants withdrawn due to an adverse event.

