7.0 Adverse Events and Product Complaints

7.1 Adverse Events

Adverse events (AEs) may occur during the treatment phase or during the follow-up phase. Adverse events occurring after the baseline assessment but before the treatment procedure will be documented in the participant's medical record but will not count as related to the study device or procedure.

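### The Safety Population is everyone enrolled, so any participant in whom the procedure was never started dilutes the device- and procedure-related event proportions

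*Combined protocol and SAP*

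**What the plan says.** Section 6.5 lists three populations. The Enrolled and Safety Populations share one definition, "all subjects enrolled in the study". Only the Evaluable Population requires treatment: "all subjects that are enrolled in the study and have received the study procedure".

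Section 5.4 fixes the moment of enrollment: "If the participant meets eligibility criteria and signs the IRB/EC approved informed consent the participant is considered enrolled". Section 5.3 places the treatment later: after the pretreatment assessments, "the study procedure should be scheduled within 30 days". Section 6.8 lists "enrolled but not treated" among the groups to be summarized.

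Section 7.1 says that events after baseline but before the treatment procedure "will not count as related to the study device or procedure". Section 6.13 says "All adverse events will be analyzed for all participants". It reports, for each event, the proportion of participants affected, and it summarizes the relationship to device and procedure. Section 6.11 gives the serious related-event endpoint through 13 weeks as a proportion with a 95% confidence interval and names no population. No section limits related-event rates to participants who were treated.

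**The concern.** A device- or procedure-related event rate should describe people who were exposed to the device or procedure. Here the set named for safety includes people who may never have been exposed. By the plan's own rule in section 7.1 they cannot contribute a related event, so their only effect is to enlarge the denominator. The bias, where there is any, runs in one direction and favors the device.

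Related serious events through 3 months are a named secondary endpoint (section 3.2). The earlier 50-participant study described in section 1.0 saw no serious events related to the device, so a count at or near zero is plausible. With a zero count the estimate carries no information beyond its upper confidence limit, and the denominator alone sets that limit.

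**Working it through.** **Inputs.** Maximum enrolled N_E = 140 (section 6.3). Related events before the procedure: none by rule (section 7.1). The number enrolled but never started on the procedure is not in the documents, so it is varied from 0 to 21 (0% to 15%). The interval method is not named, so exact (Clopper-Pearson) two-sided 95% limits are assumed.

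**The plan's own figures.** The plan states no expected safety rate and no untreated count. The one figure used here is 140. Its starting point, a minimum of 97, reproduces: a paired t-test with difference 1, SD 3 and one-sided alpha 0.025 has power 0.9015 at n = 97 by the noncentral t. Allowing for 15% loss, 97 / 0.85 = 114.1, so 115; the stated 140 is 7 participants at each of 20 sites. The 15% is an allowance for nonevaluable participants, not a forecast of untreated ones. It is used below only as an upper illustration.

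**Dilution.** Let x be the participants with a related event, N_T those in whom the procedure was started, and u = 1 − N_T/N_E. Then

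x / N_E = (x / N_T) × (N_T / N_E) = (x / N_T) × (1 − u).

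The proportion based on all enrolled is the exposed proportion multiplied by (1 − u), whatever x is.

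**Zero events.** The exact upper limit is 1 − 0.025^(1/N). For N = 140 this is 1 − 0.025^(1/140) = 2.60%; for N = 119 it is 3.05%.

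**Three participants with an event.** The limits are the 0.025 quantile of Beta(3, N − 2) and the 0.975 quantile of Beta(4, N − 3).

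| Never started (assumed) | N_T | N_T/140 | Upper limit, 0 events | 3 participants with an event (95% CI) |
|---|---|---|---|---|
| 0 | 140 | 1.000 | 2.60% | 2.14% (0.44 to 6.13) |
| 3 (2%) | 137 | 0.979 | 2.66% | 2.19% (0.45 to 6.27) |
| 7 (5%) | 133 | 0.950 | 2.74% | 2.26% (0.47 to 6.45) |
| 14 (10%) | 126 | 0.900 | 2.89% | 2.38% (0.49 to 6.80) |
| 21 (15%) | 119 | 0.850 | 3.05% | 2.52% (0.52 to 7.19) |

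The first row is what would be reported on 140 enrolled whatever the untreated number. The other rows are what the exposed participants would show. At the 15% extreme the zero-event limit differs by 3.05 − 2.60 = 0.45 percentage points, and the three-participant proportion by 2.52 − 2.14 = 0.38 points.

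**The case against.** The strongest reply has four parts.

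*The endpoint's denominator is not stated.* A reader might infer that untreated people certainly sit in the denominator of the serious related-event endpoint. The documents do not say so. Section 6.11 is silent, section 6.6 says secondary measures use available data only, and follow-up is timed from the procedure date (section 5.6), so a never-treated person has no 13-week interval. This stands. Use of the Safety Population there is inferred from its name and from section 6.13. The silence is still a reason to name the set.

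*A safety set wider than the Evaluable Population has a purpose.* A reader might infer that no one outside the Evaluable Population can have a related event. That is too strong. Someone anesthetized whose procedure is then abandoned might not count as having received it, yet could have a procedure-related event. Section 4.9.1 includes the risks of the local anesthetics and a vasovagal response, and section 5.5 asks for procedural pain from the anesthesia onward. This stands too: the problem is confined to participants in whom nothing was started.

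*Overall adverse event incidence is a different matter.* A reader might extend the point to every adverse event rate. Section 7.1.2 monitors events from enrollment to study exit, so untreated people can contribute events of any cause, and all enrolled is a defensible denominator for overall incidence.

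*Little depends on it, and it can be undone.* Study success rests on rTNSS alone (section 4.5.3), and the safety endpoint has no threshold or test. The planned participant flow diagram, counts and listings would let a careful reader recompute the rates. This limits the importance, but does not justify a headline proportion on a denominator that includes unexposed people.

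**Conclusion.** The concern holds for device- and procedure-related proportions only. If any enrolled participant is never started on the procedure, using the Safety Population as written lowers these proportions and their upper limits. The relative size for the proportions equals the untreated share: about 2% to 15% if 2% to 15% of 140 are untreated, and none if everyone enrolled is treated. In absolute terms the shift is under half a percentage point for the zero-event limit, even at the extreme.

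The conclusion rests on three things: the assumed untreated share, full enrollment of 140 with exact intervals, and, for the serious-event endpoint, the inference that the Safety Population is its denominator. The documents do not show that the bias will occur, only that the definition permits it and that untreated enrollees are foreseen. This is an inexpensive improvement of minor to modest importance.

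**What to change.** In section 6.5, define the Safety Population for device- and procedure-related rates as all participants in whom the study procedure was started, counted from first anesthetic administration so that aborted procedures are included. Name this set as the denominator in sections 6.11 and 6.13. Use the same starting point for the rule in section 7.1, so that an event after anesthesia but before energy delivery is not barred from the numerator while its participant is in the denominator.

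Keep collecting adverse events from enrollment, and list those before the procedure separately for the Enrolled Population. That listing needs the events on the adverse event form, as section 7.1.2 requires. Section 7.1 mentions only the medical record for these events and should be brought into line.

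The cost is wording. The Procedure form already records medications given before and during the procedure, and start and end times; it must also be completed for aborted procedures. The sample size and the primary analysis do not change. The downside is a slightly smaller denominator and slightly wider intervals.
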